5.8.3 Missing data

Missing data will be examined for each variable and for each cluster or individual participant. A systematic assessment of missingness will be conducted to ascertain the reason and possible mechanism for missing data by identifying the quantity of missing data and patterns within the data. Missingness will be particularly examined by cluster and between randomised arms to assess for systematic biases. Sensitivity analysis for the primary outcome of recent test for HIV will be carried out – comparing complete case analysis results with those where missing outcome status are re-classified as yes and no.

5.8.4 Outcomes

Overall numbers of ART initiations per 1,000 total adult population will be calculated for each clinic during months 1 to 12, and will be compared between intervention and control arms after adjusted for any major imbalance between the trial arms in factors such as pre-intervention ART initiation rates.

The proportion of residents accepting HIV testing will be estimated both overall and within sex, age and village strata, using population denominators from the post-intervention household prevalence survey. Participant characteristics during different time periods of the study will also be compared.

Estimates of linkage into newly accessed care will be assessed using the referral completion rate. This will compare the number of participants who disclosed positive results to CBDAs during a specific period of time to the number of participants accessing confirmatory testing following HIVST over the same time period.

The number of new HIV-positive cases will be ascertained through re-reading of returned kits and participants sharing results with CBDAs.

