1.2 Research description

The HIV STAR Malawi General Population (HIV STAR Malawi GP) study consists of a cluster-randomised trial investigating the effects of introducing HIVST to the remit of volunteers providing reproductive health services to villages in up to 5 Southern Region Districts. This research protocol is nested into the UNITAID/PSI HIV Self-Testing Africa (HIV STAR) project, which is funded to provide 34,068 episodes of HIVST in Malawi during 2016/17 with potential extension to 2018/19.

The trial population will be the catchment population (~62,500 adults) of 20 Rural Primary health clinics that have a) ART services and b) support the activities of reproductive health community-based distribution agents (CBDAs). CBDAs are lay volunteers trained and supervised by PSI to socially market reproductive health products in the rural areas.

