4.3.2 Secondary Outcome for main HIVST versus SOC CBDA intervention

The secondary outcome is: Comparison between randomisation arms of ART initiation rates for adult (16 yrs or older) cluster residents, during months 1 to 12 of intervention.

This analysis will be based on data extraction from routine ART clinic records. Residential address will be used to identify all new initiations among adults (16 years or older) living within the the wider CBDA catchment area relating to that clinic.

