HIVST will use the OraQuick ADVANCE Rapid HIV-1/2 Antibody Test. The kits, which are manufactured by Orasure, contain the HIVOFT kit, stand, buffer solution, IFUs, materials on counselling and linkage to care, and primary and secondary packaging.

A toll-free telephone number will also be provided with the HIVST kit, which can be used to access verbal pre-test information, test instructions, and results-based post-test information. Participants will also be given information on the nearest clinic for confirmatory testing and ART initiation.

The kits will be distributed for free across all of the distribution models. All distributors will receive a training package in HIVST promotion and support that has been developed in consultation with MoH HIV Department.

The study has four main phases:

- 1. Formative studies
- 2. Piloting in non-intervention area 2 villages
- 3. Cluster enumeration in all 20 ART clinics and evaluation villages
- 4. Intervention and outcome evaluation

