5.2 Cluster enumeration

5.2.1 Definition of the study population

20 primary care clinics offering ART services will be included in the intervention. The broader catchment population required for ART uptake evaluation (10 to 20 villages) will be defined in consultation with the clinic staff and PSI CBDA Project Manager. A catchment area that does not cross District boundaries and does not have major alternative ART providers will be selected if possible.

Following this, one or 2 evaluation villages within the ART clinic catchment area will be selected. Eligibility requirement for the evaluation villages include:

- Location within the catchment area of an eligible ART clinic, with the clinic acting as the most dominant source of ARTs for the village.
- Presence of at least one active PSI CBDA.
- Population of 250 to 500 adults.
- Road access for most/all of the year.
- Sufficient distance and separation from administrative boundaries and other intended evaluation villages to minimise 1) 'contamination' between HIVST and control villages, and 2) missed linkage to events from seeking HIV care at a remote clinic not included in the evaluation.
- Villages delineated by natural boundaries (e.g., rivers, roads, forests, etc.) will be preferentially selected.

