5.2.2 Baseline household surveys

All households in the evaluation villages will be visited for enumeration and invited to participate in the baseline household survey (PS401A). Village boundaries will be defined by obtained GPS coordinates.

An appointment will be made to visit the head of household or authorised individual to explain the study. All adults and older adolescents will be asked for verbal consent to participate, with verbal consent from guardians required in the case of adolescents.

As part of the baseline household survey, a household-level questionnaire of household size, age and gender composition, and socioeconomic indicators will be administered. Each adult household member will then be asked for verbal consent to participate in a brief individual questionnaire on demographic characteristics and experience with HIV testing and care.

A random selection of participants will then also be asked for written consent to complete an extended individual questionnaire on sexual behaviour, stigma, and health service utilisation, including costs. A discrete choice module will investigate user preferences for HIV delivery and linkage to care.

One in 4 household survey participants will be randomly allocated to a longer questionnaire (PS401B/PS402A), includes an approach to establishing user preferences by asking participants to make a series of trade-off choices (discrete choice experiment: DCE). Written or witnessed informed consent (or assent with guardian consent in the case of adolescents) will be obtained beforehand. Selection will be determined based on a random number generated by the electronic survey device at the time of the household survey (Choko, et al. 2015).

A post-intervention survey will be conducted with the same evaluation villages 12 months after the start of HIVST services. The post-intervention survey will consist of the household and brief individual questionnaires as well as an additional section on self-testing.

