5.6 Outcome evaluation

5.6.1 Data Capture

Four data collection channels will be employed for the impact evaluation:

- 1. Pre- and post-intervention household surveys
- 2. CBDA registers and forms
- 3. ART clinic registers and forms, and
- 4. Harms monitoring records.

Data will be collected using tablet computers and paper-based forms.

CBDA logbooks and forms

Process data on HIVST distribution by CBDAs will be captured using HIVST logbooks (date, name, village and number of test-kits taken), returned kits, self-completed questionnaires (SCQ), and self-referral cards for ART clinics.

The SCQ will include questions about the self-read HIVST result, satisfaction, coercion, and HIV testing and ART history. The returned kits will be collected and read against the SCQ by field supervisors before disposal. This will allow the study team to conduct confirmatory readings of HIVST results and provide an ongoing measure of accuracy. CBDAs will also use registers to track the age, sex and HIV and ART history of participants and the nature of support received for HIVST.

ART registers and forms

To monitor the number of referrals, HIV diagnoses and ART initiations, the study will extract routine facility records and, if applicable, self-referral cards from ART clinics serving the evaluation villages.

Harms monitoring records

Identified community leaders will provide weekly reports of deaths and any known episodes of domestic violence. CBDAs will then investigate any possible links to HIVST.

Data capture forms and questionnaires are shown in the Appendices

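### The ART-initiation rate has no stated source for its catchment denominator, and the baseline adjustment that would absorb most denominator error is applied only if the arms look imbalanced

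*Protocol*

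**What the plan says.** **Numerator.** Section 4.3.2 counts new adult initiations among residents of the "wider CBDA catchment area relating to that clinic", and states: "This analysis will be based on data extraction from routine ART clinic records".

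**Size of the area.** Section 5.2.1: "The broader catchment population required for ART uptake evaluation (10 to 20 villages) will be defined in consultation with the clinic staff" and the programme's project manager. Section 4.1 adds that this wider area is settled before randomisation.

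**Denominator.** Section 5.8.4: "Overall numbers of ART initiations per 1,000 total adult population will be calculated for each clinic during months 1 to 12". The same sentence goes on to allow adjustment for factors such as the pre-intervention ART initiation rate, on condition that the arms show a major imbalance. For the testing proportion, section 5.8.4 names the post-intervention household survey as the population source. For the ART rate it names none.

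**Who is counted.** Section 5.2.2: "All households in the evaluation villages will be visited for enumeration". Section 5.6.1 ("Four data collection channels will be employed for the impact evaluation") lists household surveys, CBDA registers, ART registers and harms records. None of these is a headcount of the catchment. The only catchment figure is the rounded total in section 1.2: "The trial population will be the catchment population (~62,500 adults) of 20 Rural Primary health clinics".

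**Analysis.** Section 5.8.5 gives each cluster equal weight and applies a t test to log cluster rates with 18 degrees of freedom. Cluster-level covariates can be added by regression at a second stage if that is judged necessary.

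**Pre-intervention data.** Section 5.6.4 plans retrospective extraction of earlier ART initiations from the 20 study clinics.

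**The concern.** The rate needs an adult population for the whole catchment of each clinic, and the protocol describes counting people in only a small part of it. The remaining population has to come from somewhere that is not named. On the log scale, an error in a clinic's population shifts that clinic's log rate by the same amount, so independent errors add to the between-cluster variance used by the t test.

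An unnamed source would be a missing detail if nothing else followed from it. The matter is one of method because the default analysis takes the error in full. The covariate that would cancel most of it, and would also remove much of the true variation between clinics, is used only if an undefined imbalance is seen.

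Whether HIVST raises demand for ART is one of the main research questions in section 3, and ART initiation is the only secondary outcome of the main comparison. What is at stake is the chance of detecting a real increase.

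**Working it through.** **1. The plan's own calculation.** Section 7.2 covers the primary outcome only. For 30% versus 45%, 250 adults per cluster and k = 0.25:

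c = 1 + (1.96 + 0.84)² × [p0(1−p0)/m + p1(1−p1)/m + k²(p0² + p1²)] / (p1−p0)²
= 1 + 7.849 × [0.21/250 + 0.2475/250 + 0.0625 × (0.09 + 0.2025)] / 0.0225 = 8.02 clusters per arm

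and 8.016 × 500 = 4,008 participants, which matches Figure 10. All 24 rows of Figures 10 and 11 reproduce. The stated sample size is correct and is not affected by this point. There is no corresponding figure for the ART outcome.

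**2. How much of the denominator is enumerated.** 62,500 / 20 = 3,125 adults per clinic on average. An evaluation village has 250 to 500 adults (section 5.2.1), so 250/3,125 = 8% to 500/3,125 = 16%. Over the whole trial, 5,000/62,500 = 8%. If catchment villages resemble evaluation villages (an assumption), 10 × 250 = 2,500 to 20 × 500 = 10,000 adults per clinic are possible. One average therefore cannot stand in for each clinic.

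**3. Effect on the unadjusted analysis (illustration).** Assumptions not in the protocol: ART rate λ0 = 0.010 per adult-year, k = 0.25 borrowed from the testing outcome, y = 3,125 adults in every clinic, rate ratio 1.5 (λ1 = 0.015), denominator error with coefficient of variation d (close to the SD on the log scale) and independent of arm. There are 10 clusters per arm.

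- k_eff² = (1 + k²)(1 + d²) − 1
- V = (1 + d²)(λ0 + λ1)/y + k_eff²(λ0² + λ1²)
- Power = Φ( √[(10 − 1)(λ1 − λ0)²/V] − 1.96 )

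d = 0: V = 0.0000080 + 0.0625 × 0.000325 = 0.0000283; √(9 × 0.000025/V) = 2.82; power 80%.
d = 0.2: k_eff² = 1.0625 × 1.04 − 1 = 0.105; V = 0.0000424; 2.30; power 63%.
d = 0.3: k_eff² = 1.0625 × 1.09 − 1 = 0.158; V = 0.0000601; 1.93; power 49%.

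| d | k_eff | Power (formula) | Power (simulated t test) | Rate ratio detectable with 80% power (formula) |
|---|---|---|---|---|
| 0 | 0.25 | 80% | 83% | 1.50 |
| 0.1 | 0.27 | 76% | 77% | 1.54 |
| 0.2 | 0.32 | 63% | 67% | 1.65 |
| 0.3 | 0.40 | 49% | 54% | 1.83 |
| 0.4 | 0.48 | 37% | 42% | 2.10 |

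The formula includes Poisson variation in the counts (10 per 1,000 × 3,125 = about 31 initiations per clinic). With assumed rates of 5 and 20 per 1,000, power falls from 70% to 34% and from 86% to 39% over the same range of d.

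**4. Bias or precision.** With no true effect, the simulated type I error of the unadjusted test stays at 4.8% to 5.2% for every d. The test's own standard error picks up the extra variance.

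**5. With the pre-intervention rate always in the model.** If both periods use the same denominator, a constant error appears in outcome and covariate alike and largely cancels. With clinic effects fully stable over time, simulated power is 97% at d = 0 and 94% to 96% for d = 0.1 to 0.4. Where stability is less than full, at an error SD of 0.2, power rises from about 66% unadjusted to between 76% and 94% as the correlation of clinic effects between the two periods goes from 0.5 to 1.

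**The case against.** - **A source may exist.** The list of phases at the start of section 5 includes "Cluster enumeration in all 20 ART clinics and evaluation villages", section 5.8.1 mentions a baseline facility assessment, and census or health-office figures are not ruled out. The choice of figures could sit in a SAP that is not shown. This stands. A reader might infer that the denominator is never measured, but the documents support only that no measurement or source is stated. Section 5.2 describes household enumeration in the evaluation villages alone.
- **Adjustment is already foreseen.** Sections 5.8.4 and 5.8.5 allow it, and section 4.1 already fixes the catchment before randomisation. This also stands, and it narrows the point to the condition attached to the adjustment.
- **False positives.** A reader might infer that population errors could create a spurious difference between arms. Errors independent of arm do not: type I error holds, and only precision is lost.
- **Size.** A reader might take the power figures as a property of this trial. They rest on assumed values, and at d = 0.1 the loss is only from 80% to 76%.
- **Quality of the earlier records.** Section 5.6.4 promises only an indication of pre-intervention initiations by clinic, and asks staff to record the village clearly from now on. Earlier village-level data may be incomplete. This stands and limits the gain from adjustment.

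**Conclusion.** The point holds in a limited form. The ART rate is defined over a catchment whose adult population has no stated source, and enumerated villages supply roughly 8% to 16% of it on the protocol's average. The default unadjusted t test takes any population error in full, while the covariate that would absorb most of it depends on an undefined imbalance.

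The consequence is lower precision on a secondary outcome, neither bias nor inflated false positives, and the primary outcome is untouched. The direction is certain for error independent of arm. The amount is not derivable from the protocol. Under the assumptions shown, unadjusted power falls from about 80% to about 65% at an error SD of 0.2 and to about 50% at 0.3. The recovery from adjustment further assumes that the error is constant over time and that clinic rates are reasonably stable from one period to the next.

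**What to change.** In section 5.8.4:

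- Make the main analysis of ART initiation a cluster-level regression of the log rate on arm and the log pre-intervention initiation rate, with the covariate always included.
- Use the same denominator for both periods, on the catchment that section 4.1 already defines before randomisation.
- Name one population source for all 20 clinics, fixed before randomisation and applied in the same way in both arms.
- Count pre-intervention initiations by the same village rule where the registers allow it, and otherwise use clinic totals.
- Report as a sensitivity analysis the log count of initiations adjusted for the log pre-intervention count. It needs no denominator, but it leaves true differences in catchment size to the covariate.

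**Cost.** One degree of freedom (17 instead of 18) and a change of wording. It draws on the retrospective extraction planned in section 5.6.4 and needs no extra enumeration, although counting by village may take more work than clinic totals. The gain is smaller if earlier village records are incomplete or clinic rates are unstable over time.

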5.8.5 Methods

All statistical analyses will be based on methods used for CRTs with a small number of clusters (Campbell, et al. 2012). The analysis for the first randomisation is based on a total of 20 clusters.

Summary measures

For binary outcomes the overall risk, combining data across clusters, and means of clusterlevel risk will be reported by intervention arm. For quantitative outcomes, the overall mean and cluster-level means will be reported by intervention arm.

Unadjusted analysis

The analysis will give each cluster equal weight. The overall risk/mean for each cluster will be calculated.

A log transformation (where necessary) will be applied to the risk/rate/mean for each cluster. For binary outcomes where there are clusters with no events, one event will be added to all clusters so that the log transformation can be conducted. The mean and standard deviation of these log risks/rates/means will be used to obtain the geometric mean (GM) and associated 95% CI for each arm of the study.

The risk/mean ratio, 95% confidence interval and p-value is estimated using a t test and the log risks/rates/means by arm, based on 18 degrees of freedom.

Adjusted analysis

Factors for adjustment will be determined as stated above.

Depending on the outcome to be analysed, logistic/linear regression will be used to adjust for confounders at the individual level and cluster level, adopting a two-stage approach.

The regression model will include terms for the individual level adjustment factors, but not study arm. For each cluster the fitted model will be used to obtain the ratio of observed to expected (O/E) events, and a log transformation will be applied to this ratio, where appropriate. A t test of the log (O/E) by arm will be used to estimate the risk ratio, 95% CI and p-value. If adjustment for cluster level factors is considered necessary, this will be conducted at the second stage using linear regression of the log (O/E) on arm and cluster level factors, with appropriate adjustment for the degrees of freedom.

Stratified (subgroup) analyses

Stratified analyses (sub-group) for the primary outcome will be pre-specified before the end of data collection,

Stratified analyses based on effect modification by cluster- or individual-level covariates will be analysed as follows: the effect of the intervention will be estimated for each strata. For individual-level covariates this will be accompanied with p-values for effect modification using the approach by Cheung et al (Cheung, et al. 2018).

6. Adverse Event Reporting and Management

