5.3 Randomisation and investigator blinding

Following baseline enumeration, ART clinic-evaluation village pairs will be randomly allocated to the intervention or control arm at a public ceremony using constrained randomisation.

Balls or discs numbered 1-N (where N represents the number of possible randomisation combinations) will be selected from an opaque bag by a stakeholder representative. The selected number will correspond to a pre-specified combination of clinics in Arms A and B.

A second opaque bag containing 2 balls – one for HIVST and one for SOC – will then be used to allocate the arm to the selected combination in a second drawing process. It will not be possible to blind participants, community workers, or their supervisors to the cluster intervention allocation, but all specimens and forms and data analysis conducted by laboratory, data, and health facility staff will be managed without reference to the intervention arm.

Outcome data will not be analysed by intervention arm until the final data analysis after completion of the trial, with the exception of data analysis by an independent statistician for presentation to the Data Safety Monitoring Board.

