5.8.2 Description of the HIVST and SOC arms in the follow-up survey

The characteristics of participants recruited into the follow-up survey, by arm (HIVST and SOC) will be described. All characteristics will be compared by arm of the trial to assess for comparability. Any variables for which there is a substantial imbalance will be noted so that final analysis can take this into account. This assessment will not be based on the results of hypothesis tests, and p-values will not be shown.

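### The 18-df t test ignores the constrained randomisation, and the imbalance rule tends to leave out the constraining variables, so inference is conservative to the extent that those variables predict the outcome

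*Protocol*

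**What the plan says.** Protocol 5.3: clinics with their evaluation villages "will be randomly allocated to the intervention or control arm at a public ceremony using constrained randomisation". A numbered ball selects one of a pre-specified set of combinations, "where N represents the number of possible randomisation combinations", and a second draw decides which group receives HIVST. The constraining variables, the balance criterion and N are not given.

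Protocol 5.8.5: "The analysis for the first randomisation is based on a total of 20 clusters". In the unadjusted analysis the effect "is estimated using a t test and the log risks/rates/means by arm, based on 18 degrees of freedom".

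For the adjusted analysis, "Factors for adjustment will be determined as stated above". The rules that stand above this are:
- 5.8.2, on the follow-up survey: "Any variables for which there is a substantial imbalance will be noted so that final analysis can take this into account".
- 5.8.4, on ART initiation: adjustment for major imbalance, with the pre-intervention initiation rate as an example.

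With individual-level factors, "A t test of the log (O/E) by arm will be used to estimate the risk ratio, 95% CI and p-value". For cluster-level factors, "If adjustment for cluster level factors is considered necessary, this will be conducted at the second stage using linear regression" of log(O/E) on arm and those factors, with the degrees of freedom adjusted.

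**The concern.** Constrained randomisation discards badly balanced allocations, so the difference between arms varies less over the allocations that could have been drawn than over all 10:10 splits. The two-sample t test does not use this. Variation between clusters that is tied to the constraining variables stays in its standard error, although the design has removed most of that variation from the difference between arms.

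The usual repair is to adjust for the constraining variables. A rule based on observed imbalance works against that, because these variables are balanced by construction. The ART outcome shows it: had the pre-intervention initiation rate been a constraint, it would be balanced and so not adjusted for, although it is an obvious predictor.

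At stake is precision: intervals wider than they need be, and power forgone.

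**Working it through.** **The plan's own figures.** 20 − 2 = 18 df. The tables in 7.2 follow c = 1 + (1.96 + 0.84)² [p0(1−p0)/m + p1(1−p1)/m + k²(p0² + p1²)] / (p1−p0)². For recent testing with p0 = 0.30, p1 = 0.435, m = 250, k = 0.25:

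c = 1 + 7.849 × (0.00084 + 0.00098 + 0.01745) / 0.018225 = 9.30 clusters per arm, as printed.

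This formula is for unmatched clusters and takes no credit for the constraint.

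**Closed-form check.** Let the constraining variables explain a share R² of the variance of the log cluster summaries (variance σ²). With exact balance, the difference between arms has variance (2/10)σ²(1−R²), while the t test estimates about (2/10)σ². The reported SE is too large by 1/√(1−R²), and the true rejection rate is about 2·P(t18 > 2.101/√(1−R²)).

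| R² | SE factor | Effective cut-off | Closed form | Simulated, tight | Simulated, loose |
|---|---|---|---|---|---|
| 0 | 1.00 | 2.101 | 5.0% | 4.8-5.5% | 4.6-4.9% |
| 0.10 | 1.05 | 2.215 | 4.0% | 3.9-4.0% | 4.0-4.9% |
| 0.25 | 1.15 | 2.426 | 2.6% | 2.5-3.0% | 2.4-3.4% |
| 0.50 | 1.41 | 2.971 | 0.8% | 0.7-0.9% | 1.1-2.2% |

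Simulation: 20 clusters, 6,000 null trials per cell, allocation drawn from the best-balanced 10% (tight) or 50% (loose) of 200 random splits. Ranges cover one and three constraining variables. Regression on arm plus those variables, with df reduced, gave 4.5-5.5% throughout.

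**On the scale of the primary outcome.** Let r be the correlation of the constraining variables with the true log cluster risk. At p = 0.30 and m = 250, the sampling variance of a log risk is 0.7/(0.3 × 250) = 0.0093, against k² = 0.0625 between clusters. So R² = r² × 0.0625/0.0718 = 0.87r², which is 0.08, 0.22 and 0.43 at r = 0.3, 0.5 and 0.7. The closed form then gives 4.2%, 2.9% and about 1.3%. Simulation with binomial sampling, over tight and loose constraints:

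| r | Type I error, t test | Power, t test | Power, adjusted |
|---|---|---|---|
| 0.3 | 3.5-4.4% | about 86% | 85-88% |
| 0.5 | 3-4% | 87-88% | 89-93% |
| 0.7 | 1-2.5% | 88-91% | 97-98% |

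Power is for a 45% increase in recent testing from 30%, the smallest effect tabulated for the primary outcome.

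**Cost of adjusting when r = 0.** About 0-2 points of power with a tight constraint or a single variable. With three variables and a loose constraint it is about 3 to 4 points for recent testing (85% v 81% in a run of 4,000 trials), and about 5 points for a 30% effect on ever testing.

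**The case against.** **The t test is not the only analysis.** A reader might infer that it is. Section 5.8.5 also provides a second-stage regression on cluster-level factors with a df correction, which is the model needed here. What is missing is a commitment to put the constraining variables in it.

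**This could be left to the SAP.** Naming covariates often is, and the SAP is not shown. In addition, 5.8.2 concerns characteristics of survey participants, and the cluster-level route has its own trigger, adjustment being judged necessary. Both points stand as limits: the protocol does not exclude the constraining variables. But it is not silent either. It fixes a selection rule by reference to imbalance, and that rule points away from them.

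**The conservatism is conditional.** A reader might infer that the true type I error is well below 5%. The documents do not support that, because they give neither the variables nor the criterion. If the variables do not predict the outcome there is no conservatism, and at r = 0.3 it is slight.

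**Planned power is not lost.** A reader might infer that the trial is underpowered. For a 45% increase in recent testing the t test keeps about 86-91%. What is lost is extra power above plan.

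**The largest losses lie elsewhere.** For a 30% increase in ever testing from 50%, power at r = 0.7 is about 61% without and 86% with adjustment. But this is a related analysis, not the primary outcome, and Figure 11 asks for 16.33 clusters per arm. Ten per arm were never sized for it, so it does not measure harm to the primary analysis.

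**An unmatched test is not itself a fault.** The pairs in 5.3 are a clinic with its village, not matched clusters, and 7.2 plans an unmatched comparison. Balance also still makes the point estimate more precise; only the reported SE misses this.

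**Conclusion.** The stated test does not reflect the stated randomisation, and the rule for choosing covariates tends to leave out those that the design makes relevant. The result is conservative inference and lost precision, never materially inflated error. The size rests on two assumptions that the protocol does not settle: how well the constraining variables predict the outcome, and how tight the constraint is. Over r = 0.3 to 0.7 the type I error of the t test runs from about 4.4% down to about 1%. For a 45% rise in recent testing, adjustment gains from nothing at r = 0.3 to roughly 10 points of power at r = 0.7. This is an efficiency point worth correcting because the correction is cheap. It does not threaten the validity of the primary analysis or its planned 80% power.

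**What to change.** State in 5.8.5 that the adjusted analysis of the primary and secondary outcomes enters the variables used to constrain the randomisation as cluster-level terms in the second-stage regression, whatever their observed balance. Remove one residual df per term: 17 df with one variable, 15 with three. Keep the 18-df t test as the unadjusted analysis.

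If too many variables were constrained to spare the df, use a permutation test over the accepted combinations, provided that the list is long enough. With N combinations and the labels settled by a second draw, swapping labels leaves a two-sided statistic unchanged. The smallest attainable p-value is then 1/N if no combination is listed in both orientations, so N = 20 could only just reach 0.05.

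The cost is one sentence before the arms are compared, and one df per variable. The t cut-off moves from 2.101 (18 df) to 2.110 (17) or 2.131 (15). If the variables turn out not to predict the outcome, the price is the small power loss shown in the working. The variables and the list must already exist for the allocation ceremony to be run.
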